## **Withdrawal of Subjects**

Patients may withdraw at any time at their discretion. Subject withdrawn from and/or terminated from research with or without their consent are those who are found to not meet inclusion/exclusion criteria, and/or are not able to complete the research protocol in its entirety, as well as those who suffer a treatment-emergent adverse effect requiring medication discontinuation. For any subjects who withdraw from research, including partial withdrawal from procedures, study data of the withdrawn subject will not be included in statistical analysis and will be shredded.

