## 5) Procedures Involved\*

*Patients coming to the oculoplastic clinic who qualify for the study based on inclusion and exclusion criteria (With upper lid retraction or asymmetry>1mm) will have the study explained to them by a research study member and they can ask questions. They will receive information on risks and benefits to research participation. For interim analysis of futility, we will do the study with BT eye drops on first 10 patients and then evaluate the results to see if there are any significant effects. If clinically significant effects are seen, then 34 patients totally (17 in BT vs 17 in saline) are included. After a written consent is obtained, External Photographs will be taken by a standard camera in standardized room light. Eyelid measurements will be done including MRD1, MRD2, PF height with the eyes in the primary position. Tear meniscus height, Schirmer I test with anesthesia and ocular staining with fluorescein will be evaluated for all patients recruited before and after eye drops are installed by the PI or resident in the clinic in the eye with greater palpebral fissure height (one eye). In each visit all these data will be obtained again. The subjects will be allocated to the treatment based on the randomization sheet provided by the biostatics department that is handed to [name], Surgical Coordinator on the 4th who will inform the PI of the patient's number. After the PI sees the patient, she will inform the resident in the clinic. The resident or the fellow in the clinic will be asked to provide the PI with the eye drop (botulinum toxin A or saline in 1 cc syringes without needles) while not informing of the contents. The research team([name], [name], [name], [name]), also blinded to the study will gather the data and take the necessary photos (double Blinded).*

*Potential toxicity or life-threatening toxicity with topical botulinum toxin is unlikely.*

*Pressure on the lacrimal sac by the patients for 2 minutes will be done to minimize systemic absorption.*

*Patients will be provided a phone number to call if any complications occur.*

*BOTOX®, JEUVEAU, XEOMIN, and DYSPORT are Crystalline preparations of BT type A, FDA approved drugs for many indications including periocular wrinkles. Saline eye drops will be also used as placebo.*

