*If any patient develops side effects that require a medical need to unblind and treat, the PI can find out which group was the patient allocated (unblinding) by contacting [name].*

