#### Adverse Events and Serious Adverse Events

Treatment-emergent adverse events, defined as any event, not present prior to the initiation of the drug treatment or any event already present that worsens in either intensity or frequency following exposure to the drug treatment, will be monitored and reported throughout the study. Treatment emergent adverse scale will be graded as the following:

- Mild: Transient or mild discomfort (<48 hours) to the subject; no medical intervention/therapy required.

- Moderate: Mild to moderate limitation in activity of the subject; no or minimal medical intervention/therapy required.

- Severe: Marked limitation in activity of the subject, some assistance usually required; medical intervention/therapy required including possible hospitalization.

Serious adverse events are defined as those which result in death, hospitalization, persistent or significant incapacity or substantial disruption of the ability to conduct normal life functions (aka disability), or congenital anomaly / birth defect.

Previously reported treatment-emergent adverse effects are described further in the risks section below.

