## **6) Risks to Subjects\***

The primary risks to the subjects are adverse reactions to the medication. These risks are explained to patients prior to their arrival to the oculoplastic clinic. Previously described potential adverse reactions when injecting the periocular area are dull and transient headaches with malaise, Ptosis. Severe reactions seen in injections of BT in non-periocular areas such as anaphylaxis, soft-tissue edema and dyspnea are rare in occurrence. (28) Injection of BT in neck: Hoarseness and dysphagia). (28)

All are reversible side effects. (28)

Subjects may have mild ptosis in due to botulinum eye drop but it will eventually improve. Also, the drop can be used in the opposite eye to give symmetry.

Potential psychosocial risks to subjects include time taken from their day to undergo tests, potentially missing work, and anxiety or discomfort from the eye drop instillation process. This study is not collecting sensitive information, thus no potential risk to reputation or legal risks should occur.

Subjects will be instructed to call immediately for an appointment if they notice a change in their vision, eye redness, or the development of pain in either eye. Care will be taken by all study members to prevent the occurrence of any adverse events.

There are no well-controlled studies of BT-A eye drops in pregnant women, and the risks to the fetus or embryo are unknown/unforeseen. One prior publication reported abortion or fetal malformations which have been observed in rabbits after injection (29) however, another larger prospective study found no increased risk of malformations associate with BT-A for chronic migraine during pregnancy in 45 patients (30). No studies have been performed evaluating topical BT ophthalmic solution. BT is classified as US FDA pregnancy category C. (29)

- US FDA pregnancy category C: Animal reproduction studies have shown an adverse effect on the fetus and there are no adequate and well-controlled studies in humans, but potential benefits may warrant use of the drug in pregnant women despite potential risks.

Participants will be informed of the above information and reserve the right to decline participation in the study. We will not be following pregnancy outcomes.

Unanticipated problems or complications will be reported to the IRB according to posted guidelines.

Risks of the study are listed above and will be minimized by the following:

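### The withdrawal rule does not separate stopping drug from stopping follow-up: with one scheduled application, terminating a treated patient saves no scheduled exposure and gives up scheduled visits, and declining a single test could discard a patient's data

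*Combined protocol and SAP*

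**What the plan says.** The Withdrawal of Subjects section opens its list of removals with "Subject withdrawn from and/or terminated from research with or without their consent are those" and then names three grounds. The first is failing the eligibility criteria. The second covers patients who "are not able to complete the research protocol in its entirety". The third is an adverse effect: "as well as those who suffer a treatment-emergent adverse effect requiring medication discontinuation". The object of the sentence is the research, not the treatment.

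The following sentence deals with subjects who withdraw, "including partial withdrawal from procedures, study data of the withdrawn subject will not be included in statistical analysis and will be shredded".

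The unnumbered Procedures Involved section has one application step (Part 2, one eye), followed by return visits at which the baseline measurements are repeated (Part 3). Study Timelines gives six visits in all, five of them after baseline. No repeat dose is scheduled. The only other exposure mentioned is in section 6, which allows a drop in the opposite eye for symmetry.

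The Adverse Events section says that treatment-emergent events "will be monitored and reported throughout the study". No section keeps a terminated patient on the visit schedule.

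**The concern.** In a repeat-dose trial, taking a patient off drug after an adverse effect limits further exposure. Here the scheduled dose has already been given and cannot be taken back, so what remains to be stopped is observation. A rule that ends participation because of a treatment-emergent event works against the commitment to monitor such events throughout the study.

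This matters because the route is new. Section 3 (Background) says that there are no previous studies of this kind, and section 6 repeats the point for the topical solution in its pregnancy paragraph. The day 3 to day 90 visits are the planned source of safety data for this route and carry the primary outcome, change in palpebral fissure height.

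The completion ground does not say whether it means a patient who can no longer take part, or one who misses a single visit or test. The partial-withdrawal clause then puts the data of a patient who stays in the trial at risk over one declined procedure.

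**Working it through.** **Inputs from the documents.** One application; follow-up on days 3, 7, 14, 30 and 90 (primary outcome timeframe); 17 per group, alpha 0.05, power 80% (Number of Subjects). One scheduled application is an inference: the phrase single dose does not appear, but only one instillation step is described.

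**The plan's sample size.** It cannot be reproduced, because no effect size, SD, sidedness or dropout rate is given. Solving backwards, 17 per group at 80% power implies a standardized difference of 0.99 (two-sided, two-sample t-test). An assumed difference of 1.0 SD needs 16.7, so 17 per group.

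**Follow-up lost if terminated at a visit.** Scheduled doses avoided: 0 in every row.

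| Terminated at day | Later visits lost (of 5) | Scheduled days lost |
|---|---|---|
| 3 | 4 | 90 − 3 = 87 |
| 7 | 3 | 90 − 7 = 83 |
| 14 | 2 | 90 − 14 = 76 |
| 30 | 1 | 90 − 30 = 60 |

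**Partial withdrawal.** Fissure height is the sum of MRD1 and MRD2 and does not depend on the Schirmer test. A patient who declines one Schirmer test still has 1 + 5 = 6 fissure-height values. Under the clause as worded, all 6 could be excluded and destroyed.

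**Completion ground, by reading.** Assume independent misses with probability q per visit; q is not in the documents.
- One missed visit counts: 34 × [1 − (1 − q)^5]. For q = 1%, 2%, 5% this is 34 × 4.9%, 9.6%, 22.6% = 1.7, 3.3, 7.7 patients.
- Two must be missed: 34 × [1 − (1 − q)^5 − 5q(1 − q)^4] = 0.03, 0.13, 0.8 patients.
- The patient can already attend no more visits: no later visits are lost.

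**Illustration of efficacy impact only.** Assume 17 v 17, a true effect of 1.0 SD of the change, a two-sided two-sample t-test, and removals from the toxin arm only. The Data Analysis section names a paired test; the two-sample test is used because the comparison is 17 v 17. For random removal, power comes from the noncentral t distribution with noncentrality √[n1·n2/(n1 + n2)]: √8.5 = 2.92 for 17 v 17, falling to √(14 × 17/31) = 2.77 for 14 v 17. The selective columns come from 200,000 simulated trials. Cells show the mean estimate in SD and the power.

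| Removed | At random | At random from the more affected 8 of 17 | Most affected |
|---|---|---|---|
| 0 | 1.00; 80.7% | as at left | as at left |
| 1 | 1.00; 79.4% | 0.95; 75.5% | 0.89; 72.6% |
| 2 | 1.00; 78.0% | 0.89; 69.0% | 0.79; 63.6% |
| 3 | 1.00; 76.4% | 0.83; 61.0% | 0.70; 53.9% |

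These figures apply to visits after removal, or to all visits if earlier data are also destroyed. They leave out the first 10 patients, who all receive toxin and have no comparison arm.

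**The case against.** The strongest reply is that the adverse-effect ground does nothing. With one dose there is no scheduled medication to discontinue, so the phrase looks like wording carried over from a repeat-dose protocol. That largely stands: it may seldom or never trigger, and the zero row of the table then applies. But a ground that is either idle or harmful is still worth deleting, and the completion ground does not depend on dosing.

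Second, someone unable to complete the protocol has usually stopped attending. On that reading no later visits are lost, and the larger counts above need the harshest reading.

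Third, there is other safety cover: a complication phone number, call-in appointments, IRB reporting, and a route to unblinding ("If any patient develops side effects that require a medical need to unblind and treat"). Participants are also patients of the same clinic. This cover is real, but none of it is a scheduled study measurement.

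Two stronger readings are tempting and are not supported. A reader might infer that the rule removes responders, since lid lowering is both the intended effect and a possible adverse effect. No section makes ptosis a ground for removal, and section 6 describes it as mild and improving. A reader might also infer that every terminated patient's earlier data are destroyed. The sentence is written for subjects who withdraw; its reference to the withdrawn subject may reach terminated patients, but it does not say so.

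**Conclusion.** The point holds as an inexpensive improvement to the wording. The Withdrawal of Subjects section does not distinguish stopping drug from stopping follow-up. Where either ground operates after the drop, it reduces no scheduled exposure and costs up to four visits once the day 3 visit has taken place. As worded, the partial-withdrawal clause could also discard all fissure-height data for one declined test.

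This rests on two readings: that one application is scheduled, and that termination from research ends study visits. Both are the plain sense of the text, though neither is stated outright. The bias and power figures show what selective removal could do under assumed numbers and are not a forecast. With no removal rate in the documents, the size and direction of any bias are unknown, and zero is possible.

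**What to change.** In Withdrawal of Subjects:
- Delete the completion ground and the adverse-effect ground.
- Limit the ineligibility ground to patients found ineligible before the drop is given. Otherwise it would still terminate treated patients.
- State that every treated patient stays on the day 3 to day 90 schedule, for the measurements they accept and the investigator considers safe, unless they withdraw consent for follow-up. Schirmer or fluorescein testing could, for example, be omitted in an affected eye.
- State that an adverse effect stops only further drops, such as the opposite-eye drop in section 6.
- Delete the clause that extends exclusion and destruction to partial withdrawal from procedures, so that patients with incomplete measurements stay in the analysis with the data they have.

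In the risk-minimization list of section 6, which says that the study will be discontinued for a negative effect, add that enrolment and dosing then stop but treated patients complete safety follow-up.

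The cost is a wording amendment. The visits are already scheduled, and no staff or procedures are added. The downside is some incomplete visit data to handle in the analysis. How to treat data after full withdrawal of consent is a separate question.

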## **Study Timelines**

Recruitment will occur for 1 year. After interim analysis, the study will end once 34 patients are recruited. The study length for the patient is expected to be at least 3 months, with the recruitment/baseline visit and follow up visits at 3 days, 1 week, 2 weeks, 1 and 3 months from the first visit, for a total of 6 visits. The study is expected to last about 1 year from the time of IRB approval to completion of all study activities, including analysis of identifiable data.

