- Study will be discontinued if subjects experience any negative effect from the medication
- Patients with a known sensitivity or history of adverse reaction to BT or similar medications will be excluded from the study

As with any study, there is a risk of confidentiality breach. The research members will assign each patient a specific ID number and place this information on a separate spreadsheet. No names will be used in the forms. Presentations and publications will not identify individual patients.

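### Excluding and shredding the data of every subject who withdraws, even in part, can make the analysis depend on outcome, and the loss cannot be undone

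*Combined protocol and SAP*

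**What the plan says.** **Withdrawal of Subjects.** For a subject who withdraws, "including partial withdrawal from procedures, study data of the withdrawn subject will not be included in statistical analysis and will be shredded". The sentence before it lists who counts as withdrawn or terminated, with or without consent. The list includes those whose adverse effect requires stopping the medication and those who "are not able to complete the research protocol in its entirety". No exception is made for safety data.

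**Design.** The first 10 patients all receive botulinum toxin, with no control. If clinically significant effects are seen (no threshold is given), 34 patients follow, 17 per group (section 5, Procedures Involved, and Number of Subjects). There are "follow up visits at 3 days, 1 week, 2 weeks, 1 and 3 months from the first visit, for a total of 6 visits", and all measurements are repeated at each. Study Timelines adds: "After interim analysis, the study will end once 34 patients are recruited". The primary outcome is change in palpebral fissure height, and Data Analysis names a paired t-test. The documents state no missing-data method, dropout allowance or replacement rule.

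**Adverse effects.** Section 6, Risks to Subjects, says: "Subjects may have mild ptosis in due to botulinum eye drop but it will eventually improve". It continues: "Also, the drop can be used in the opposite eye to give symmetry". Among its risk-minimising steps is: "Study will be discontinued if subjects experience any negative effect from the medication". The adverse events section introduces mild, moderate and severe grades ("Treatment emergent adverse scale will be graded as the following"), but no stopping or withdrawal rule uses them.

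**The concern.** An exclusion rule is harmless only if leaving has nothing to do with outcome. Here a lowered lid is both the effect sought and the side effect expected. A patient who leaves because the lid dropped too far takes a large response out of the data; one who leaves because nothing happened takes out a null response. With 10 uncontrolled patients deciding whether the randomised stage opens, one or two such losses could matter.

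In the randomised stage, removing subjects after treatment means the groups compared are no longer those that were randomised. Shredding makes this permanent: nobody could later run an intention-to-treat analysis or test how sensitive the result is to the exclusions. The protocol itself says topical botulinum toxin ophthalmic solution has not been studied, so safety observations from these patients are hard to replace.

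**Working it through.** **1. The plan's own figure.** Number of Subjects gives 17 per group for alpha 0.05 and 80% power, without an effect size or SD, so it cannot be reproduced, only solved backwards. Two-sided, normal approximation: d = (1.960 + 0.842) × √(2/17) = 0.96. With the two-sample t-test, d = 0.99. For the paired test named in Data Analysis, 80% power needs 0.72 SD with 17 pairs or 0.50 SD with 34. With 10 patients, a paired test at 0.99 SD has 80% power (79.5%).

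**2. Direction of bias (invented values).** Eight patients at −1 mm and two at −3 mm average (8 × −1 + 2 × −3)/10 = −1.4 mm; without the two, −1.0 mm. Eight at −1 mm and two at 0 mm average −0.8 mm; without the two, −1.0 mm. The first deletion understates the effect and the second overstates it.

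**3. Worst-case selective loss in the 10-patient look.** Simulation, 100,000 runs: 10 normal changes with SD 1, the k most extreme on one side deleted, then a two-sided 5% paired t-test on the rest, counting significant falls.

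| Deleted | No true effect, least improved deleted: mean; significant fall | True fall 0.99 SD, most affected deleted: mean; significant fall |
|---|---|---|
| 0 | 0.00; 2.5% | −0.99; 80% |
| 1 | −0.17; 8.5% | −0.82; 68% |
| 2 | −0.32; 18.7% | −0.67; 54% |

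Loss unrelated to outcome costs less: at 0.99 SD, power is 74% with 9 patients and 67% with 8. The drop from 67% to 54% is the part due to selection.

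**4. Randomised stage.** Assumed loss of 10% or 20%, two-sample t-test, d = 0.99: 17 × 0.9 = 15.3 per arm gives 75%; 17 × 0.8 = 13.6 gives 70%. Replacing the lost numbers would need 34/0.9 = 37.8, so 38, or 34/0.8 = 42.5, so 43 (44 with equal arms). This restores numbers and does not remove bias.

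**5. Only if non-completion counts as withdrawal, and one missed visit counts as non-completion.** With chance m of missing each of 5 follow-up visits, the share missing at least one is 1 − (1 − m)^5.

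| m | Share missing one or more | Of 10 | Of 34 | Left per arm | Power |
|---|---|---|---|---|---|
| 2% | 9.6% | 1.0 | 3.3 | 15.4 | 76% |
| 5% | 22.6% | 2.3 | 7.7 | 13.2 | 68% |
| 10% | 41.0% | 4.1 | 13.9 | 10.0 | 56% |

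Keeping attended visits at m = 5% leaves about 17 × 0.95 = 16 per arm at each visit, with power about 78%.

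**6. Safety (assumed events).** If 2 of 10 patients are harmed, both withdraw and their events are recorded nowhere else, the data show 0 of 8: one-sided 95% upper limit 1 − 0.05^(1/8) = 31%. The full data, 2 of 10, give 51% (exact binomial).

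**7. The stopping sentence, read literally for the whole study.** The chance of at least one event in 10 patients is 1 − (1 − p)^10. For assumed rates of 1%, 5%, 10% and 20% it is 10%, 40%, 65% and 89%.

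**The case against.** Several stronger conclusions are tempting, and the documents do not support them.

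- *The stopping sentence also distorts the 10-patient decision.* It removes no patient and shifts no estimate; at most it ends the trial first. It may also mean only that subject's participation, which would fit the per-subject withdrawal rule and the per-patient item next to it. The defect is ambiguity.
- *One missed visit erases a subject.* This joins the list of who is withdrawn to the shredding sentence, which speaks of those who withdraw. The link is reasonable but not explicit, and a missed visit is not plainly a withdrawal. Step 5 therefore stays conditional. Partial withdrawal from procedures is explicit.
- *The look would hide harm and so change the decision.* The written criterion is clinically significant effects; no adverse-event rate enters it. Events are to be monitored and reported throughout, and complications go to the IRB, so some safety information may survive. What remains is that safety data not already reported could be shredded.
- *Losing one or two patients reverses the decision.* With no threshold stated, no reversal can be shown. In the first example of step 2, any threshold of 1 mm or less gives the same answer. Only could is supported.
- *Removed subjects are not replaced.* Recruitment ends at 34, but Data Analysis says 34 are required, which may mean 34 analysable. The text simply gives no rule.
- *The power figures are the trial's power.* They rest on a back-solved effect and a two-sample test, while the plan names a paired test.

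The drop also appears to be given once, so few patients may have a medication to discontinue. That narrows one route to withdrawal and leaves the others. None of these points alters what the withdrawal sentence tells the team to do with the data.

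**Conclusion.** The concern holds for the withdrawal rule. Followed as written, it excludes subjects after treatment for reasons that can be related to the primary outcome, in both the 10-patient look and the randomised comparison, and it destroys the data needed to check the effect. The bias could run either way. Its size depends on how many withdraw and why, which the documents do not say. The worst cases for two selective losses among 10 are a false-positive chance of 18.7% against 2.5%, or power of 54% against 80% for a true fall of 0.99 SD. In the randomised stage, an assumed 10% to 20% loss would take a nominal 80% power to about 75% to 70%, if the back-solved effect and a two-sample test apply.

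The stopping sentence is a separate, secondary matter. Read literally, it would end the trial for the mild ptosis that the same section accepts, so the team has no usable rule.

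**What to change.** **Withdrawal of Subjects.** Replace the exclusion-and-shredding sentence with a rule that:

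- keeps all data collected up to withdrawal or partial withdrawal;
- uses them in the 10-patient look, with all 10 treated patients accounted for;
- uses them in the final analysis by randomised group, each visit including every subject measured at that visit;
- never destroys safety data.

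**Risks to Subjects (secondary).** Reword the stopping sentence to say whether it applies to the subject or the study, and tie it to the mild, moderate and severe grades already defined. The exact limit is for the IRB; a strict one is defensible for an unstudied route.

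**Cost.** Two sentences reworded, consent wording that data collected before withdrawal are kept (the consent pages were not available, so whether they already say this cannot be checked), and IRB agreement. No extra patients, visits or measurements are needed. The change should be in force before any withdrawn subject's data are shredded.

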## Procedures Involved

**We anticipate that the procedures listed below will take about 30 to 40 minutes per patient. Each patient will have a complete ophthalmologic exam. Except as noted, the procedures below are not considered standard of care and are being conducted for the study alone.**

- A. Part 1: Pre-treatment data collection
  - External photographs, MRD1, MRD2, palpebral fissure height, tear meniscus height, Schirmer I test with anesthesia and ocular staining with fluorescein will be recorded.
- B. Part 2: Botulinum toxin or Placebo topical application
  - Subjects will be randomized to receive either 15 units of botulinum toxin A (BOTOX), incobotulinum toxin A (XEOMIN), prabotulinum toxin A (JEUVEA), the equivalent of 45 units of abobotulinum toxin A (DYSPORT) or balanced saline placebo in one eye after 10 patients are included for the interim analysis with BT eye drops topically on the surface of the eye
  - Then based on the randomization results, the examiner will apply botulinum eye drops or saline to the one of the subject's eyes.
- C. Part 3: Post-treatment data collection
  - Subjects will come back in 3 days, 1 week, 2 weeks, 1 & 3 months after they receive the treatment or control.
  - At each visit, subjects will have the measurements above again.
- D. Part 4: Data analysis
  - Data will be recorded and stored in a secure Microsoft Office Excel (Microsoft Corporation, Redmond, WA, U.S.A.) spreadsheet. Data will be graphically analyzed and represented with Adobe Photoshop (Adobe, Inc., San Jose, CA, U.S.A.).
  - Data assessed will involve assessing pre- and post-treatment MRD1 and MRD2, investigator-assessed measurements of ocular surface and tearing.
  - User performing analysis will be blinded to which eye received study drug.

Follow-up outside of the patient's next routine clinic visit will be needed for 3 days, 1 week, 2 weeks and 1 & 3 months. Patients who do have symptoms concerning any post-procedural complications will be instructed to notify study staff immediately. A phone number will be provided.

Outcomes Measures:

Primary outcome:

Outcome Measure Title: Change in palpebral fissure height

Outcome Measure Description: Palpebral fissure height will be calculated from the sum of marginal reflex distance 1 and 2 measured by the researcher.

Outcome Measure Timeframe: Baseline, day 3, 7, 14, 30 & day 90.

Secondary outcomes:

Outcome Measure Title: Change in eye ocular surface and tearing

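### Withdrawn patients, including those who decline a single procedure, are dropped from the analysis and their data shredded, which can bias the randomised comparison and prevents later repair

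*Combined protocol and SAP*

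**What the plan says.** The rule is in Withdrawal of Subjects. Its scope is "For any subjects who withdraw from research, including partial withdrawal from procedures", and its consequence is that "study data of the withdrawn subject will not be included in statistical analysis and will be shredded".

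The sentence before it lists those withdrawn or terminated with or without their consent: patients found ineligible, patients who "are not able to complete the research protocol in its entirety", "as well as those who suffer a treatment-emergent adverse effect requiring medication discontinuation".

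Other sections bear on the point:

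- Procedures Involved describes a randomised comparison with saline and five return visits: "Subjects will come back in 3 days, 1 week, 2 weeks, 1 & 3 months after they receive the treatment or control". All measurements are repeated at each visit.
- Number of Subjects gives 17 per group for alpha 0.05 and 80% power. Study Timelines ends the study when 34 are recruited. Data Analysis gives 34 as the number needed and names a paired t-test.
- Adverse Events and Serious Adverse Events says that treatment-emergent events "will be monitored and reported throughout the study".
- Section 6, Risks to Subjects, says "Unanticipated problems or complications will be reported to the IRB according to posted guidelines". It also says "Study will be discontinued if subjects experience any negative effect from the medication".

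No section defines an intention-to-treat set, a missing-data method or a sensitivity analysis, and nothing overrides the shredding rule.

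**The concern.** Randomisation protects the comparison only while patients are analysed as allocated. This rule removes them for things that happen afterwards. Its trigger is wide: read literally, a patient who declines one later Schirmer test also forfeits every palpebral fissure height already recorded.

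Loss related to both arm and outcome is plausible here. Section 6 expects that the drop may cause mild ptosis, and a lower lid is also what the primary outcome measures. A patient with a large effect could therefore be one who leaves. Loss of patients with poor outcomes would push the estimate the other way.

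An ill-chosen analysis set can be corrected later, but destroyed data cannot. The rule also makes no exception for adverse-event records. If these count as study data, a safety summary by arm would omit the patients who left, even though individual complications go to the IRB.

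**Working it through.** **1. Scope of the rule.** Partial withdrawal is covered expressly. Whether the rule also reaches the patients listed in the sentence before it is likely but not certain. The adverse-effect ground may rarely apply, because Procedures Involved describes a single application. The statement in section 6 about discontinuing after any negative effect would widen that ground if it refers to the patient's own participation. The two statements must be reconciled.

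**2. The plan's own figure.** The 17 per arm cannot be reproduced, because no effect size, SD or sidedness is given. It can only be back-solved. For a two-sided two-sample t-test at 0.05 with 17 v 17 and 80% power:

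- normal approximation: d = (1.96 + 0.84) × √(2/17) = 0.96 SD
- exact noncentral t: d = 0.991 SD

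This assumes that the first 10 patients, all given BT for the interim look, are outside the 34. It uses a two-sample test although the plan names only a paired one, because the arms contain different patients.

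**3. Loss unrelated to outcome**, d = 0.991 SD:

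| Analysed per arm | Power |
|---|---|
| 17 | 80.0% |
| 16 | 77.4% |
| 15 | 74.5% |
| 14 | 71.4% |

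No dropout margin is stated, but a hidden one cannot be excluded. If 17 was raised from 16, the implied effect is 1.02 SD and 16 per arm still gives 80%.

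**4. Outcome-related loss.** Simulation with 17 per arm randomised and unit SD. Each patient has a latent withdrawal score correlated with the outcome at 0.5, or at 1 as the worst case. The most extreme scorers are dropped and the rest compared by t-test. A higher outcome means a better response.

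| Scenario | True effect | Estimate, SD (worst case) | Rejection rate (worst case) |
|---|---|---|---|
| No loss | 1 SD | 1.00 | 81% |
| 2 best BT responders lost | 1 SD | 0.90 (0.79) | 70% (64%) |
| Best BT responder and poorest saline patient lost | 1 SD | 0.89 (0.78) | 70% (64%) |
| 2 poorest BT outcomes lost | 0 | 0.10 (0.21) | 6% (about 10%) |
| Poorest outcome lost in each arm | 0 | 0.00 (0.00) | 5.4% (6.9%) |

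**5. Bias or smaller numbers?** With a true effect of 1 SD, 17 v 17 gives 80.7% power. Losing two BT patients at random (15 v 17) gives 78.0%. So of the fall to 70% in the second row, about 3 points (80.7 − 78.0) come from smaller numbers and about 8 (78.0 − 70) from selective loss.

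**6. If one missed visit counted as not completing the protocol.** The text does not settle this. With five return visits and independent misses at rate p, the share excluded is 1 − (1 − p)^5. At p = 2%, 5% and 10% this is 9.6%, 22.6% and 41.0%, or about 3, 8 and 14 of 34.

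**The case against.** The strongest points on the other side are these.

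- *Shredding describes paper, and the data sit in a spreadsheet.* This is fair as to physical destruction: deletion of spreadsheet rows is not mentioned. But the rule covers study data without exception, and exclusion from the analysis applies in any case.
- *The route to arm-related loss is thin.* With one application, discontinuing medication may seldom arise, and nothing in the documents shows that good responders would leave. The number lost and the correlation of 0.5 are assumptions. This stands as a limit on the size. The defect remains, because voluntary and partial withdrawal are covered outright.
- *The adverse-event conflict is conditional.* An event can be reported to the IRB before a file is destroyed. This is true for single reports, but it does not secure a summary by arm.
- *The figures do not model the named paired test, and the milder effects are modest.* Both are true. The need to retain data does not depend on which test is used.
- *Equal loss in both arms is not always harmless.* This is correct. The zero bias in the last row of the table holds for a constant treatment effect and need not hold if response to BT varies between patients.
- *The consent form may promise destruction.* Consent pages are not in the copy reviewed, so this must be checked, above all for patients already enrolled.

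**Conclusion.** The concern holds, and the rule is wrong as written: it is not merely a missing detail. Followed literally, it removes randomised patients for post-randomisation events and destroys the data that would show how much this mattered. It must be fixed.

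That conclusion rests on the text alone. The size of the bias is uncertain: about 0.1 SD for two selectively lost patients in one arm at a correlation of 0.5, and about 0.2 SD at worst. It would be nil if loss were unrelated to outcome. Confidence is high on the core rule. It is lower on how far the rule reaches patients terminated for other reasons, and on whether adverse-event records are included.

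**What to change.** Replace the shredding sentence with wording such as:

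> Data collected up to withdrawal are kept, as the consent allows. A patient who declines one procedure or misses a visit stays in the study for the remaining measurements if willing. All randomised patients are analysed in the arm assigned, using all available visits. Withdrawals are reported by arm and reason, with a sensitivity analysis for outcome-related missing data. Adverse-event records of all treated patients, including those who withdraw, are kept and reported by group.

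In addition:

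- Reword the ground about not completing the whole protocol, so that incomplete data alone does not remove a patient from the analysis.
- Reconcile Withdrawal of Subjects with the adverse-event section and with both statements in section 6.
- Name the primary analysis. A likelihood-based mixed model is one suitable choice. It assumes that missingness is explained by observed data, hence the sensitivity analysis.
- State whether 17 per arm includes a dropout allowance. If not, either say that 80% power refers to 17 analysed per arm and give the power at the expected loss, or randomise 17/(1 − loss) per arm: 18, 19 or 22 for an assumed 5%, 10% or 20%. Extra patients restore power but do not remove bias.

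The cost is a protocol wording change, a check that the consent permits keeping data after withdrawal, and some missing-data modelling. Adding patients is optional: 2 to 10 in total (36 to 44 instead of 34).
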